10.9 Follow-Up on AEs

All non-serious AEs should be followed until they are either resolved, i.e., returned to baseline or until the end of the post-treatment FU period (3 weeks after last IMP administration) whichever comes first. AEs meeting one of the serious criteria (including AEs of Special Interest), still ongoing after ending trial participation, should be followed on a regular basis, according to the investigator's clinical judgment, until the event has been resolved or until the investigator can assess it as chronic or stable.

If an ongoing SAE changes in intensity, relationship to IMP or as new information becomes available and/or known for the event, a FU SAE report form should be completed and sent to the sponsor within 24 hours of the change in SAE assessment.

If the investigator becomes aware of an SAE after the long-term FU period with a suspected causal relationship to the IMP, the investigator should report this SAE within the same timelines as for SAEs during the trial.

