¹⁰ If CSF sample is positive for abnormal cells or outside reference ranges for any of the following: 1. total protein 2. glucose 3. cell count, it must be repeated within 4 weeks of the sample at screening. If abnormal CSF glucose (CTCAE \geq Grade 2) is obtained, a fasting serum glucose is to be obtained at next patient visit. At week 26, the CSF analysis should include cytology only.

¹¹ Treatment with potassium iodide and Cytomel should be initiated 1 week prior to each ¹³¹I- omburtamab infusion in a cycle and continue until 2 weeks after ¹³¹I- omburtamab infusion in the same cycle..

¹² Thyroid protection should be initiated 1 week prior to IMP administration. See section 7.2.5 for further details.

¹³ Thyroid protection should be initiated 1 week prior to next IMP administration – this is only applicable for week 4 and not week 8. See section 7.2.5 for further details.

¹⁴ Beginning 24 hours before ¹³¹I-omburtamab administration please see section 6.1.2.

¹⁵ Given 1-2 hours prior to ¹³¹I-omburtamab administration, including oral acetaminophen/paracetamol and antihistamine (e.g., diphenhydramine), please see section 6.1.2¹⁶
Drawn and held for culture if elevated body temperature after dosing suggests infection rather than expected response to intracerebroventricular dosing.

¹⁷ Dose reduction: 50% (25 mCi) for patients < 1 of age and 33% (33.5 mCi) for patients age 1 year to < 3 years of age, respectively.

¹⁸ Non-SAE's captured from signing the informed consent form (ICF) to dosing should be recorded as medical history. AEs should be reported until 3 weeks after the last IMP administration. SAE's should be captured from signing the ICF. Starting at week 4 (for patients receiving only one cycle) and starting at week 8 (for patients receiving both cycles) only SAEs considered related to ¹³¹I-omburtamab or new onset of cancers regardless of causality should be reported.

¹⁹ Limit to therapy related to cancer.

²⁰ In case fertile women (experienced menarche prior to screening or during treatment, until week 8) are enrolled; pregnancy testing should take place at screening, at week 4 and week 8, and at follow-up at week 26.

²¹ Follow-up at week 26 (24-29 weeks after first treatment) and Long-term follow-up visits at Weeks 52, 78, 104, 130 & 156 (\pm 4 weeks) can be done at referral site.

²² If done at referral site imaging parameters as required in the Imaging Manual should be followed to the extent possible.

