6 DESCRIPTION OF DESIGN AND TRIAL POPULATION

6.1 Overall trial design and plan

This single-arm, open-label, non-randomized trial includes a screening period followed by treatment and observation periods. At least 32 patients are expected to be enrolled. Before entering the screening period, patients are recommended to have received salvage therapy including surgery, irradiation (preferable craniospinal) and high dose chemotherapy (recommended modalities listed in Appendix 2).

Patients without an objective disease progression (as determined by radiographic examination) 4 weeks after the first infusion and without clinically significant Grade 4 toxicity, are eligible for a second dosing cycle. ^{131}I -omburtamab will be administered via an indwelling intracerebroventricular access device (e.g. Ommaya). In order to avoid an additional procedure and burden to the patient, it can be considered to place the intracerebroventricular access device in connection with the recommended tumor resection procedure (see section 13.4).

After ^{131}I -omburtamab treatment, safety and efficacy will be assessed as described in the flow charts in Table 1 Schedule of time and events with follow-up at week 26 followed by long-term follow up for up to 3 years with regards to survival. An interim analysis, evaluating the dosimetry and pharmacokinetic endpoints as well as available safety and efficacy data, has been conducted on data from patients having received at least treatment cycle 1 (both dosimetry and treatment dose) prior to January 1st, 2020. Starting January 1st, 2020, no further patients will be administered dosimetry doses. After completion of the interim analysis, the dosimetry doses have been removed from treatment cycles. After this, a treatment cycle will take 4 weeks, compared to the previous 5 weeks cycle and will include a treatment dose only followed by an observation period and post-treatment evaluations.

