6.1.4 Duration of treatment

A single treatment cycle will last 4 weeks and includes premedication, intracerebroventricular ^{131}I -omburtamab administration [REDACTED], an observation period, and post-treatment evaluations (see Figure 1 One ^{131}I -omburtamab treatment cycle after the interim analysis).

Figure 1 One ^{131}I -omburtamab treatment cycle after the interim analysis

[figure not shown]
Patients without Grade 4 toxicity and without objective disease progression (as determined by neurologic and/or radiographic examination) by MRI at week 4 in cycle 1 will be eligible to receive a second ^{131}I -omburtamab dosing cycle. Patients with Grade 3 toxicity will receive a second dosing cycle at the discretion of the investigator. For patients presenting with ongoing Grade 3 or 4 myelosuppression at week 4, a delay of dosing cycle 2 for up to 8 weeks can be introduced. Dose delay may be enforced at the discretion of the treating physician.

In case of a subsequent relapse in the CNS/LM during the follow-up period, re-treatment to target minimal residual disease can be considered and allowed in case the patient/parents provide written consent to this. In these cases, it is recommended that patients undergo the salvage treatment as specified in Appendix 2 before subsequent administration of ^{131}I -omburtamab. The administration of ^{131}I -omburtamab in these cases must follow the scheme of the treatment cycle as illustrated in Figure 2.

Patients who complete at least one treatment cycle will be evaluable. All patients who complete at least one treatment cycle (one dose of ^{131}I -omburtamab) will form part of the dataset. However, patients who do not continue to the second treatment cycle (for whatever reason) will be registered as “early treatment discontinuation” in the eCRF. Patients receiving both treatment

cycles of ^{131}I -omburtamab will be registered as “completed treatment” in the eCRF. All evaluable patients will first enter a follow-up period through week 26 (Figure 2) and thereafter the long-term follow-up where patients will be evaluated every half year for up to 3 years post- ^{131}I -omburtamab treatment where after the trial is ended.

)

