6.9.3 Treatment discontinuation criteria

A patient must be discontinued from treatment if:

- Treatment-related CTCAE Grade 3 or 4 anaphylaxis.

- CTCAE Grade 4 neurotoxicity.
- Development of obstructive or symptomatic communicating hydrocephalus
- Unexpected, IMP-related and clinically significant Grade 4 toxicity.
- Disease progression before cycle 2.
- The investigator requests discontinuation of treatment for medical or safety reasons, including lack of treatment response; or
- The patient receives prohibited therapy and/or undergoes prohibited procedures during the trial.

Diagnosis of chemical meningitis (symptoms of clinical meningitis but cultures for infective agents were negative) in which either: a) event is non-responsive to IV steroids, b) radiologic or operative intervention was indicated, or c) presence of focal neurologic deficit. A patient discontinued from treatment should as soon as possible attend the week 4 or 8 visit as applicable, and subsequently be followed at the short and long-term follow-up visits. The investigator should follow any SAE still ongoing after discontinuation until the event has been resolved or the investigator assesses the SAE as being chronic or stable.

A patient should be withdrawn from the trial if:

- The patient or legal guardian withdraws consent for any reason;

If the patient is withdrawn from the trial, the investigator should:

- Ensure the safety of the patient.
- Offer the best possible treatment outside of the trial.

Furthermore, after withdrawal for any reason, the investigator, in consultation with the patient/legal guardian, will recommend future treatment based on clinical practice at the investigational site.

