8.1.2 Secondary endpoints

1. CNS/LM PFS at 6 and 12 months will be estimated based on the time from first treatment dose to CNS/LM progression or death from any cause. Patients alive without CNS/LM progression at time of analysis, will be censored at last date of disease evaluation without evidence of progression.
2. OS at 12 months will be estimated based on the time from first treatment dose to death by any cause. Patients alive at time of analysis, will be censored at last date known to be alive.
3. ORR assessed as a combination of partial response and complete response as defined by the Response assessment in Neuro-Oncology (RANO) group criteria for brain metastasis (Lin et al, 2015) or leptomeningeal metastases as defined by EANO-ESMO criteria (Le Rhun et al, 2017). ORR will be assessed at 6 months after the first treatment dose of ^{131}I -omburtamab
4. ORR according to CSF cytology. Response is defined as a complete response when CSF converts from positive at baseline to negative after treatment with ^{131}I -omburtamab
5. Whole-body, organ, blood, and CSF radiation dosimetry.
6. Pharmacokinetic analysis of activity in blood and CSF including derivation of best-fit uptake and/or clearance parameters (half-times, maximum value) of time-activity concentration curves and of I-131 residence times (i.e., cumulated activity) concentrations (in $\mu\text{Ci}\cdot\text{h/g}$).
7. The frequency, type, and duration of treatment-emergent severe adverse events and serious adverse events, including clinically significant laboratory abnormalities. All adverse events will be graded according to Common Terminology Criteria for Adverse Events (CTCAE), version 4.0.
8. Performance assessment to monitor gross changes in neurological function is performed at week 26 and subsequently every 6 months during trial period.
9. The rate of ADA occurrence assessed three weeks after the first and second treatment dose of ^{131}I -omburtamab

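### Endpoint 7 includes the duration of severe adverse events, but follow-up of non-serious ones is not required beyond 3 weeks after the last dose

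*Combined protocol and SAP*

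**What the plan says.** Secondary endpoint 7 (protocol 8.1.2, repeated in the synopsis) is "The frequency, type, and duration of treatment-emergent severe adverse events and serious adverse events, including clinically significant laboratory abnormalities". Severe events are named beside serious ones, so the endpoint is not confined to serious events.

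Section 10.9 follows non-serious events until they resolve or "until the end of the post-treatment FU period (3 weeks after last IMP administration) whichever comes first". Table 1, footnote 18, sets the same limit on reporting: "AEs should be reported until 3 weeks after the last IMP administration". After that, only related serious events and new cancers are reported. Neither place treats Grade 3 or higher differently.

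Serious events and events of special interest are followed until resolved, chronic or stable (10.9), and 10.8 has events of special interest reported as serious. The special-interest list in 10.4 covers Grade 3 or higher neurotoxicity, severe device-related infection and chemical meningitis. Myelosuppression is a named risk in 10.7 but is not on that list.

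Section 10.8 also says that forms for non-serious events are signed at resolution, or by the end of the trial at the latest. Section 12.4 summarises numbers of events and of patients. It gives no method for duration and no rule for events still open.

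**The concern.** A duration needs an end date. For a severe but non-serious event that is open 3 weeks after the last dose, the protocol does not oblige the site to look for one. If the cut-off is then taken as the end of the event, the duration is too short. If the event is treated as censored, the censoring time depends on how many cycles were given.

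The plan itself foresees such events. Section 6.1.4 provides, at just that time: "For patients presenting with ongoing Grade 3 or 4 myelosuppression at week 4, a delay of dosing cycle 2 for up to 8 weeks". At stake is how long an expected toxicity lasts at severe grade, which the endpoint sets out to describe.

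**Working it through.** The plan states no figure on this point, so there is none to reproduce. The check is a comparison of passages plus calendar arithmetic.

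**1. Which events are exposed.** Start from all severe events. Remove serious events and events of special interest, which 10.9 follows further. Remove events that have resolved by the cut-off. Under 10.6.4 a change of grade opens a new record, so an event that has fallen below Grade 3 by the cut-off has its severe period closed; remove those too. What remains is non-serious, not of special interest, and still Grade 3 or higher at the cut-off.

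**2. When the cut-off falls.** Inputs: dosing on day 1 of a 4-week cycle (7.1.1); a limit of 3 weeks after the last dose (10.9). With time counted in days after dose 1, cut-off = day of last dose + 21.

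- One cycle: 0 + 21 = 21 days, which is study day 22, the first day of week 4.
- Cycle 2 on schedule: 28 + 21 = 49 days.
- Cycle 2 given d days late: 28 + d + 21 = 49 + d days. Section 6.1.4 does not say from which date its limit on the delay is counted, so no upper figure is given here.

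These figures apply to the first course. Re-treatment after a CNS/LM relapse (6.1.4) would move the last dose.

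**3. Whether the cut-off depends on toxicity.** Section 6.1.4 admits to cycle 2 "Patients without Grade 4 toxicity and without objective disease progression". Section 6.1 has patients who are "without clinically significant Grade 4 toxicity, are eligible for a second dosing cycle". Section 6.9.3 stops treatment for "Unexpected, IMP-related and clinically significant Grade 4 toxicity". These conditions are not the same and need to be reconciled. Under any of them, toxicity partly decides whether a second dose is given, and so when follow-up of a cycle-1 event ends. Toxicity that prevents cycle 2 leaves the 21-day cut-off in place; a delay followed by dosing moves the cut-off later. The net direction cannot be derived from the documents.

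**4. What is observed afterwards.** Footnote 21 places the next visit: "Follow-up at week 26 (24-29 weeks after first treatment". That is 24 × 7 = 168 to 29 × 7 = 203 days after dose 1. Measured from the cut-off:

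- One cycle: 168 − 21 = 147 to 203 − 21 = 182 days later.
- Two cycles on schedule: 168 − 49 = 119 to 203 − 49 = 154 days later.

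Table 1 marks no hematology at week 26 or later, and 11.1 limits blood counts to screening and the treatment cycles. Section 9.2.1 speaks of counts up to the week-26 follow-up. The passages disagree on whether counts are planned in this interval.

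**5. Illustration only.** The documents give no onset days or durations. Assume exponential durations, onset 7 to 14 days after the last dose and a median of 7 to 28 days. The share still open at the cut-off is 0.5^((21 − onset)/median):

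- Onset 7, median 7: 0.5^(14/7) = 25%.
- Onset 14, median 28: 0.5^(7/28) = 84%.

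The width of this range shows that the share cannot be fixed from the documents.

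**The case against.** The strongest reply is section 10.8. A form that may stay unsigned until resolution or the end of the trial leaves room for a later end date, and 10.6.6 refers to separate completion instructions for ongoing events. This stands in part. A reader might infer that these dates are not collected at all. The documents support only that they are not required. A sign-off deadline does not tell a site to keep following an event that 10.9 has released.

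It can also be said that the exposed group is narrow. This stands: serious events and events of special interest are followed further, and a laboratory abnormality counts as an adverse event only if it needs active management (10.1.1). A reader might infer that the group is mainly cytopenia. That is plausible from 6.1.4, 10.4 and 10.7, but no frequencies are given.

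Third, no Kaplan-Meier analysis of event duration is planned, so there is no such analysis to fault. This stands. Section 12.1 leaves detail to the SAP, and a rule for open events could be placed there. Such a rule could censor these events, but it could not oblige sites to record later dates.

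Last, the two sentences on grading in 10.6.4 might be read as a contradiction. They can be read together, as the worst grade within a record and a new record at each change, and 12.4 already counts a patient once per preferred term. What remains is that split records shorten durations and raise the number of events.

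**Conclusion.** The point holds as a minor one. Endpoint 7 asks for a duration that 10.9 and footnote 18 do not require sites to complete, and 10.8 does not settle the matter. The cut-off for a cycle-1 event is 21 days after dose 1 with one cycle, 49 with cycle 2 on schedule, and later if cycle 2 is delayed and then given. The truncation may therefore be informative. A reader might go further and infer that severe events will look shorter, or longer, than they are; the documents do not fix a direction or the number of events.

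Patient-level incidence, serious events, events of special interest, and events no longer severe at the cut-off are unaffected. The last of these assumes that duration means time at severe grade, as the new-record rule in 10.6.4 suggests. The day counts assume dosing on the scheduled days and no re-treatment.

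**What to change.** - **10.9 and footnote 18:** for each Grade 3 or higher event still ongoing 3 weeks after the last dose, require the resolution date, or ongoing status at the existing week-26 visit, taken from blood counts and contacts already available. Align 10.8 with this.
- **12.4:** summarise duration with unresolved events censored at the last assessment, not counted as ended. Join contiguous records created by grade changes under 10.6.4 into one episode, for both duration and event counts. State whether duration means time at Grade 3 or higher or time to resolution.
- **9.2.1, Table 1 and 11.1:** reconcile them on blood counts up to week 26.

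The cost is a little extra data entry, partly through referral hospitals. No visit is added, so some resolution dates will be known only as an interval. Week 26 is a common limit from dose 1 but not from the last dose: with cycle 2 on schedule, 168 − 28 = 140 to 203 − 28 = 175 days remain after dose 2. Follow-up therefore stays somewhat unequal, which is a further reason to censor open events.

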11 LABORATORIES

Nuclear scanning (whole-body planar gamma camera scans) and radioactivity measurements in CSF and blood will take place on-site following qualified procedures outlined in respective manuals. The calculation of the absorbed radiation doses will take place centrally following a predefined methodology. Pharmacokinetic parameter derived from radioactivity concentration vs. time data will be calculated centrally.

A detailed description of the procedures for sampling, handling, storage, and measurement of the specimen and all material such as test tubes and labels will be provided in the Technical Binder. Blood samples for biochemistry and hematology will be analyzed by local laboratories.

11.1 Clinical chemistry and hematology

Chemistry Panel

Liver and renal function tests (ALT, AST, alkaline phosphatase, TSH, T4, albumin, total bilirubin, total protein, LDH, BUN, and creatinine), serum glucose and serum electrolytes (sodium, potassium, chloride, and bicarbonate). If abnormal serum glucose (CTCAE \geq Grade 2) is obtained, a fasting serum glucose is to be obtained at next patient visit.

Hematology Panel

Complete blood count will be performed during screening and during all treatment cycles with regards to hematocrit, hemoglobin, Mean Cell Hemoglobin (MCH), Mean Cell Hemoglobin Concentration (MCHC), Mean Cell Volume (MCV), platelets, red blood cells (RBC), WBC, basophils, eosinophils, lymphocytes, monocytes and neutrophils. All Grade 4 laboratory abnormalities must be retested within 24 hours of receiving results.

12 STATISTICAL METHODS AND DETERMINATION OF SAMPLE SIZE

12.1 General Overview

The data will be summarized in tables, as appropriate, showing the number of patients with non-missing data (n), mean, standard deviation, median, minimum, and maximum for continuous data and showing counts and percentage for categorical data. Data will also be listed as deemed appropriate. All statistical analyses will be performed and data appendices will be created by using SAS version 9.0 or later.

All statistical tests will be two-sided with an α level of 0.05.

The Statistical Analysis Plan (SAP) will describe in detail the analyses presented below. Furthermore, handling and presentation of data including baseline data and other trial assessments will be described in the SAP. The selection of an appropriate control group from available external data is briefly described below but will be described in full detail in the SAP. Patient characteristics that may be considered in the selection of the control group include, but are not limited, age at diagnosis, MYCN amplification status, International Neuroblastoma Staging System stage at diagnosis, International Neuroblastoma Pathology Classification (favorable vs. unfavorable), time to first relapse, site of relapse, and lactate dehydrogenase level.

12.2 Populations of Interest

- Full Analysis Set

The full analysis set (FAS) will include all patients enrolled in the trial who begin an infusion of ^{131}I -omburtamab

- Per Protocol Analysis Set (PPS)

The PPS will include all FAS patients who have no major protocol violations.

Additional patients with other protocol violations may be uniformly excluded on the basis of data review. The precise reasons for excluding patients from the PPS will be fully defined and documented before data lock

- Safety Analysis Set

The safety analysis set will include all enrolled patients who receive at least one dose of IMP

- External control group

External controls will be primarily obtained from a query to the Central German Childrens Cancer Registry (CGCCR). CGCCR initiated in 1980, registers approximately 2,000 children per year who are diagnosed with a malignant disease. CGCCR receives patient data from all paediatric oncology centers across Germany. 99% of all paediatric patients diagnosed with cancer in Germany were included in the national trials, with continuous update of the clinical data within the CGCCR.

The CGCCR data will be used to obtain an estimate of the 3-year survival rate in a contemporary systemically treated cohort of children. To explore the development of systemic treatment we will employ cut-offs in 2000 and 2004.

[REDACTED]

[REDACTED]

[REDACTED]

[REDACTED]

[REDACTED]

